## **III. Objectives**

**Objective 1: To determine the effect of immediate postpartum initiation of DMPA on breastfeeding.** We hypothesize that administration of DMPA immediately postpartum (i.e., before hospital discharge) will not impair breastfeeding compared to administration beginning at 12 weeks post-delivery. To increase the likelihood of detecting a negative effect if one exists, we will evaluate the primary outcome, timing of lactogenesis stage II (onset of copious milk secretion, usually occurring within 96 hours postpartum), as well as a range of secondary outcomes: breastfeeding duration, perceived need for supplementation, use of supplementation, perceived adequacy of milk production, and infant anthropometric measures, including body composition with whole-body air displacement plethysmography (OSUWMC site only). Sensitivity analysis will evaluate 1) excluding women in the open control arm and 2) determining whether the findings differ by race.

**Objective 2: To determine the effect of immediate postpartum initiation of DMPA on contraception use.** We hypothesize that putative DMPA use (i.e., blinded assignment to intervention or placebo arms) will put women on a better trajectory of contraception use by intervening during a time when they likely are highly motivated to avoid pregnancy. In contrast, women who are assigned to start DMPA after a delay risk losing motivation to initiate use. To test this hypothesis, we will compare prevalence of use of a highly-effective contraceptive method at 12 months post-delivery between women in the intervention and placebo arms versus the open control arm. Secondary outcomes will include DMPA use at 12 months. Sensitivity analyses will evaluate 1) whether the findings differ by race and 2) whether the findings differ after restricting the intervention and placebo arms to the subset of women who believe that they were in the intervention arm.

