**Figure 1. Study design**

The study will be partially blinded: participants and study staff, including the study statistician, will be blinded as to the assignment for those in the intervention and placebo arms. In contrast, no one will be blinded as to assignment to the open control arm. (Note that it is not feasible to maintain blinding for the open control arm even among the data analysts given the planned grouping of the arms for the data analyses.) DMPA has a duration of protection of 12 weeks. Women in the intervention or placebo arm will be counseled to refrain from initiating hormonal contraception in the next 6 weeks and to refrain from initiating DMPA in the next 12 weeks. Study staff will use the "Contraceptive choice information sheet" to explain the contraceptive methods that participants can use depending on whether they are assigned to an arm that receives a shot or the arm that does not receive a shot. All participants will be counseled to use condoms post-delivery to avoid a repeat pregnancy (as they either received no shot or could have received a placebo shot). Participants will receive a supply of condoms for either 12 weeks (intervention or placebo arm) or 6 weeks (open control arm), and will be referred to receive DMPA at either 12 weeks (intervention or placebo arm) or 6 weeks post-delivery (open control arm).

Data collection, which will occur at enrollment and through 12 months of follow up, will involve 1) questionnaires on demographics, characteristics and behaviors, lactogenesis, breastfeeding and contraception use and 2) infant anthropometric measures (Table 1).

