For secondary outcomes (breastfeeding duration, perceived adequacy of milk production, etc.), we do not have *a priori* set noninferiority margins, and thus a traditional superiority analysis will be conducted (test for significant differences using t-tests or chi-squared tests as appropriate). We will report two-sided 95% CIs for all outcomes so that post-hoc noninferiority analyses could be conducted (i.e., to evaluate whether the CI covers a specified noninferiority margin).

**Analysis of Objective 2.** A traditional superiority analysis will be used to compare rates of use of a highly effective method of contraception (defined here as DMPA, implant, IUD, sterilization, pill, patch, or ring) at 12 months post-delivery among women in the intervention or placebo arm versus those in the open control arm. An intent-to-treat analysis will be conducted using a chi-squared test to compare the percentages of women using contraception in each group (intervention + placebo versus open control). As a sensitivity analysis, we will repeat this analysis using logistic regression in order to account for potential confounders such as maternal age, parity, gravidity, socioeconomic status, sexual activity, and prior contraceptive history. We will also repeat analyses restricting those in the intervention or placebo arm to the subset of

women who believe that they received DMPA at enrollment regardless of the accuracy of their belief as an additional sensitivity analysis. Furthermore, we will evaluate whether the relationship between immediate postpartum DMPA initiation and contraception use at 12 months differs by maternal Black race.

Given that the contraception use outcome is measured at 12 months, we anticipate some missing data; however, we have no reason to believe dropout will be differential across arms. Thus, we will assess sensitivity of results to missing data using multiple imputation analyses under both missing at random and missing not at random assumptions. The secondary outcome (DMPA use at 12 months) will be analyzed with similar methods.

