**Sample size.** Sample size was based on providing high (90%) power for the primary outcome of Objective 1 (time to lactogenesis II), while also ensuring appropriate power for Objective 2. We assumed that all groups would have a mean of 65 hours with a common standard deviation of 18 hours, based on a previous study, which was consistent with past research. Setting the noninferiority margin at 6 additional hours, **with a type 1 error rate of 0.05 (two-sided 95% CI), we require 143 women randomized to each group to achieve 90% power.** As this outcome is measured very soon after randomization, we expect to have it measured on all randomized women. However, we note that even if we have a small amount of missing data for this outcome, we will still have high power. For example, if we have 10% missing data (i.e., time to lactogenesis II measured on 128 women per group), we will still have 87% power. Additionally, this sample size ensures adequate power for our sensitivity analysis comparing intervention to placebo (i.e., excluding women in the open control arm); we will have 80% power for the noninferiority analysis comparing these two groups (under the same assumptions as stated above).

The sample size justified for Objective 1 also will provide high power for Objective 2, which will be assessed using traditional superiority analyses. Based on a recent analysis of data from the National Survey of Family Growth, we assume that the rate of highly effective contraceptive use will be 50% in the open control arm. We conservatively assume a 20% attrition rate at 12 months, thus will have n=114 women in the open control arm and n=228 women in the combined injection arms (DMPA; placebo). With this sample size of randomized women, we will have 81% power to detect a contraceptive use rate of 66% in the intervention/placebo group, corresponding to a relative risk of RR=1.32.

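### The Objective 2 belief-restricted sensitivity analysis filters only the injection arms on a post-randomisation belief, so it is not a randomised comparison and can show or hide an effect

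*Combined protocol and SAP*

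**What the plan says.** The main Objective 2 analysis is set out in the combined protocol and SAP, section V.E, Analysis of Objective 2: "An intent-to-treat analysis will be conducted using a chi-squared test to compare the percentages of women using contraception in each group", with intervention and placebo pooled against open control. The outcome is use of highly effective contraception at 12 months.

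The same section then repeats the analysis with both injection arms limited to "women who believe that they received DMPA at enrollment regardless of the accuracy of their belief", and describes this repeat "as an additional sensitivity analysis". Section III, Objective 2, announces it as an evaluation of "whether the findings differ after restricting the intervention and placebo arms to the subset of women who believe that they were in the intervention arm".

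Neither place restricts the open control arm, and no matching subset could be formed there: under the design description in section V.A, "no one will be blinded as to assignment to the open control arm". The text plans no comparison of believers with non-believers and gives no caution on interpretation. It does not settle when belief is asked, because in section V.E the reference to enrollment can attach either to the injection or to the belief. The descriptions of the enrollment and follow-up questionnaires in section V.D mention no belief item, though the forms themselves are not in the documents.

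**The concern.** Belief about the injection is a post-randomisation variable that exists in two arms out of three. Selecting on it in those arms and comparing the selected women with all open controls gives up the protection of randomisation on one side only.

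Belief may well be related to later use. Objective 2 rests on motivation driving contraceptive use, and motivation may also colour what a woman thinks she received. Section VI.E lists bleeding irregularities among the known effects of DMPA, so belief may partly track the drug actually given. If belief were asked during follow-up, contraceptive experience could shape it as well.

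The adjusted logistic model, if it is also applied to the subset, names maternal age, parity, gravidity, socioeconomic status, sexual activity and contraceptive history as example covariates. It names neither motivation nor symptoms after the injection.

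At stake is the reading of this one analysis. A difference between it and the main result could come from selection alone, and agreement between the two could conceal a bias. The plan gives the reader no means of telling which has happened.

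**Working it through.** **Inputs from section V.E, Sample size.** 143 randomised per arm; 20% attrition at 12 months; 114 open controls and 228 injection-arm women evaluable; 50% use in open control; 66% as the alternative; stated power 81%. The two-sided 0.05 level is stated there for Objective 1 and is assumed to apply to Objective 2.

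**Inputs not in the documents (assumed).** f, the share of injection-arm women who believe they received DMPA; D, the use rate of believers minus that of non-believers.

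**Step 1: reproduce the plan's figure.** 0.8 × 143 = 114.4 and 0.8 × 286 = 228.8, matching 114 and 228 rounded down. For the two-proportion z-test with pooled null variance:

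- pooled rate = (114 × 0.50 + 228 × 0.66)/342 = 0.607
- SE under the null = √(0.607 × 0.393 × (1/114 + 1/228)) = 0.0560
- SE under the alternative = √(0.25/114 + 0.2244/228) = 0.0564
- power = Φ((0.16 − 1.96 × 0.0560)/0.0564) = Φ(0.89) = 81.3%, against the stated 81%

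**Step 2: what the restriction does when assignment has no effect.** Let use be 50% in every arm. Since 0.50 = f × (believer rate) + (1 − f) × (non-believer rate), the believer rate is 0.50 + (1 − f) × D. The restricted contrast therefore has expected value (1 − f) × D instead of zero.

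**Step 3: rejection rate of the restricted test.** The test compares 228 × f believers with 114 open controls. Example with f = 0.5 and D = 0.20, so 60% vs 50% with 114 each:

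- null SE = √(0.55 × 0.45 × 2/114) = 0.0659
- alternative SE = √((0.24 + 0.25)/114) = 0.0656
- Φ((0.10 − 1.96 × 0.0659)/0.0656) ≈ 0.328; adding the opposite tail (about 0.0002) gives 32.9% to three figures

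| Share believing (f) | Gap (D) | Believers' use | Believers (n) | RR vs 50% | Rejects |
|---|---|---|---|---|---|
| 50% | 0 | 50% | 114 | 1.00 | 5.0% |
| 50% | 10 points | 55% | 114 | 1.10 | 11.7% |
| 50% | 20 points | 60% | 114 | 1.20 | 32.9% |
| 50% | 30 points | 65% | 114 | 1.30 | 63.1% |
| 40% | 20 points | 62% | 91 | 1.24 | 40.3% |
| 60% | 20 points | 58% | 137 | 1.16 | 24.4% |
| 75% | 20 points | 55% | 171 | 1.10 | 13.2% |

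Simulation with 200,000 runs agreed for the cases tried: 5.1%, 32.9% and 63.4% at f = 50% with gaps of 0, 20 and 30 points, and 24.4% at f = 60% with 20 points. On the same simulated data the intent-to-treat comparison rejected about 5% throughout.

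**Step 4: negative gaps.** With 50% in the control arm the calculation is symmetric, so a gap of −20 points at f = 50% gives 40% vs 50% and the same rejection rate in the wrong direction. A real effect can also be masked: if injection-arm use were truly 66%, a gap of −20 points at f = 50% gives believers 0.66 − 0.5 × 0.20 = 56%, an apparent difference of 6 points instead of 16.

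**Step 5: power.** With no selection and 66% vs 50%, the restricted test has 69% power at f = 50% and 77% at f = 75%. A single randomised arm against open control (114 vs 114) also has 69%: Φ((0.16 − 1.96 × 0.0654)/0.0645) = Φ(0.49).

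**The case against.** The strongest reply is that little rests on this analysis. It is labelled as a sensitivity analysis and sits beside adjusted regression, an evaluation by race and multiple imputation. No error rate, power claim or decision rule depends on it. That stands, and it limits the importance of the point. It does not make the comparison randomised, and section III still presents it as a check on whether the findings differ.

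A reader might go further and infer that the belief subset tests the mechanism that Objective 2 hypothesises, so that its bias threatens the Objective 2 conclusion. The documents do not support this. Section III defines putative use as blinded assignment to either injection arm, and tests it by comparing both full injection arms with open control. Nor do the documents say that a larger effect among believers would be taken as confirmation.

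It is also fair to say that the sizes are assumed. The 63% figure needs a 30-point gap produced by selection alone. Section V.B requires every participant to want DMPA before discharge, which may narrow differences in motivation. With no gap there is no bias.

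Finally, the timing of the belief question may be fixed on forms outside these documents. A reader might infer that belief is asked late and shaped by the outcome; the text leaves that open and does not show it.

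**Conclusion.** The point holds as a design flaw in one supporting analysis. Filtering two arms on a post-randomisation belief and keeping the third whole does not give a randomised comparison, and it is biased by (1 − f) × D whenever believers and non-believers differ in use. The main intent-to-treat test of Objective 2 is untouched.

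Under the illustrative assumptions, the restricted test's false-positive rate runs from 5% with no gap to 63% with a 30-point gap and half believing, and is 13% with 75% believing and a 20-point gap. The sign of the gap is unknown, so the bias may go either way. The share believing, the gap and the 50% rate in all arms under no effect are assumptions. The documents support the direction of the argument but no particular size.

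**What to change.** In section V.E, and correspondingly in section III:

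- Make the supportive analyses for Objective 2 the two randomised contrasts that the design already provides, placebo vs open control and DMPA vs open control, with estimates and 95% confidence intervals and no confirmatory claims.
- State beside them that the injection and open control arms also differ in referral timing and condom supply (12 vs 6 weeks, sections V.A and V.D). Placebo vs open control therefore does not isolate the effect of believing that one had an injection.
- Relabel the belief-restricted comparison as exploratory and non-randomised, and use belief recorded once, soon after the injection. State where it is recorded.
- Weighting open controls by their predicted probability of belief is optional. It handles measured baseline covariates only and cannot remove causes of belief that arise after baseline, such as noticed drug effects.

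The cost is revised wording, a little more analysis and, if no early belief item exists, one added question. Each arm-specific contrast has about 69% power for 50% vs 66% with 114 per arm, against 81% for the pooled test. That equals the power of the restricted analysis if half the women believe, and is below its 77% if three-quarters do.

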## VI. Ethical Considerations

### A. Potential Risks

This study poses no more than minimal risk to participants. Participants may experience psychological risks associated with answering questions about sensitive topics or reporting attitudes and behaviors, such as their contraception use.

The study intervention under evaluation (i.e., administration of DMPA for contraception within 48 hours of delivery among women intending to breastfeed their infants) is not contraindicated per the medical eligibility criteria for contraception use issued by the U.S. Centers for Disease Control and Prevention. However, while clinical practices often provide DMPA to breastfeeding women, many settings – including the study site – do not routinely offer DMPA to this group during the immediate postpartum period. Thus, the current trial is warranted to address the gap between U.S. guidelines and routine clinical practice. The trial design is ethical given that the U.S. guidelines permit immediate initiation of DMPA among breastfeeding women. Furthermore,

IRBs have approved the conduct of trials involving randomizing women to start contraception at different times with condoms provided for use in the interim (see our trial approved by the CDC IRB as well as other examples.)

We will not perform any genetic testing.

## **B. Protections Against Risk**

**Several measures have been implemented to minimize the risks to individuals from trial participation.** First, during the consent process, women will be advised that they are free to decline study participation and that they can decline to participate without affecting their care at the facility. Participants also will be informed that if they are uncomfortable at any time, they can decline to answer any questions, participate in any study activity, or discuss any topic. If indicated, participants will be referred for counseling services.

Participants also will be informed of their freedom to terminate the interview or visit at any time without affecting their routine health care at the facility. All interviews will take place in a private setting by interviewers who have been trained thoroughly on the importance of confidentiality, the procedures to protect a participant's confidentiality, and the penalties associated with breaches of confidentiality.

Participants' personal information will be kept confidential. Access to the roster with identifiers will be limited to authorized study personnel. Participants' privacy and the confidentiality of data will be protected through training of interviewers and other study staff; conducting all interviewing in private; storing study materials in a locked room when not in use; and securing computer files that include identifiers or study data. A unique code will be used to identify the participant's study records. The linkage between the PINs and the participants' identifying information will be maintained in a REDCap form. These linkages will be destroyed after the primary study findings have been published.

## **C. Potential Benefits of the Research to Human Subjects and Others**

The trial provides no direct benefits to the research participants. Participants and others may indirectly benefit in the future if the trial shows no difference in immediate initiation of DMPA compared to initiation at 6 weeks postpartum in terms of the effects on breastfeeding and infant development.

The potential risks involved in trial participation are reasonable in relation to the anticipated benefits.

## **D. Importance of the Knowledge To Be Gained**

The research will provide important information on the effects of immediate postpartum initiation of DMPA among breastfeeding mothers and their infants.

## **E. Incidents and Incident Reporting**

**Study staff will record information on any adverse events (AEs) that are classified 1) as possibly, probably, or definitely related to study participation and as unexpected or 2) as serious.** Adverse events (AEs) are defined as any untoward health-related reaction, effect,

toxicity, or abnormal laboratory result that a study participant experiences during the course of a study that is new or a worsening of a baseline condition.

An *unexpected* AE is one whose specificity or severity is not listed in the DMPA package insert (i.e., bleeding irregularities, bone mineral density changes, cancer risks, thromboembolic disorders, ocular disorders, ectopic pregnancy, and anaphylaxis). Information on expected AEs will be recorded on study data collection forms, but these events will not be reported to the relevant IRBs and NIH unless the event is also serious or is an unanticipated problem involving risks to subjects or others (UPIRTSO).

An AE is considered *serious* if it is fatal or life-threatening, requires in-patient hospitalization or prolongation of an existing hospitalization, results in a persistent or significant disability or incapacity, is a congenital anomaly or birth defect, jeopardizes the participant or requires intervention to prevent one of the outcomes listed above, or any other event deemed serious by the investigator. Study personnel will report any AE to the PI, who will determine 1) its relatedness to study participation and 2) its seriousness.

All serious adverse events (SAEs) will be reported in an expedited manner to the PI. If it is determined that the SAE is unanticipated and anything other than “not related” (i.e., possibly, probably or definitely related), then the PI, or designee, will notify the IRBs of record and the NIH of the event. Non-serious AEs will be recorded on data collection forms but do not require expedited reporting unless they are classified as UPIRTSO.

UPIRTSO are any events or information that were unexpected and indicate that research procedures caused harm to participants or others or indicate that participants or others are at increased risk of harm. An unanticipated problem may involve any aspect of the research study and could involve anyone including participants, research staff, or others not directly related to the study. AEs that are unexpected and related and protocol violations are specific examples of UPIRTSO. (Not all AEs are UPIRTSO, and not all UPIRTSO are AEs.) Examples of other UPIRTSO include 1) a breach of confidentiality; 2) a change to the protocol taken without prior IRB review to eliminate an apparent immediate hazard to a research participant; 3) halting of the study by a sponsoring agency; and 4) a participant complaint that indicates unexpected risks or that cannot be resolved by the study team. Any possible UPIRTSO will be recorded on the appropriate log and report form. The PI will decide whether the incident meets the definition of UPIRTSO and, thus, requires prompt reporting to the IRBs and NIH.

All adverse events will be managed according to the standard of care for the clinical practice and the judgment of the on-site clinicians.

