## **F. Data Safety and Monitoring Plan**

**The Regulatory and Ethics Core of The Center for Clinical and Translational Science (CCTS) at OSU will assemble a Data Safety Monitoring Committee (DSMC) – consisting at minimum of a research ethicist / research subject advocate, biostatistician, and obstetrician-gynecologist – to independently monitor the safety of the study. The DSMC will be chaired by [name], who is Professor in the Department of Internal Medicine at OSU and the Director of the Regulatory Program at CCTS. The DSMC will convene before study initiation and, during this initial meeting, the DSMC will provide recommendations regarding the protocol application and will develop and approve the DSMC Charter for the trial. After trial initiation, the DSMC will review the accumulated data after an initial subset of participants have been enrolled and after half of the participants have been enrolled. The DSMC**

will evaluate participant safety and study conduct and progress and will make recommendations to the sponsor and investigators concerning the trial continuation, modification or termination. No specific stopping guidelines will be presented with the data, and stopping early for safety reasons will be based on the judgment of the DSMC.

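### The adverse-event recording sentences in Section VI.E contradict each other and the event definition does not name the infant, so non-serious events may be captured unevenly between the injection arms and open control, and in infants only by partial routes

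*Combined protocol and SAP*

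**What the plan says.** Section VI.E (Incidents and Incident Reporting) opens, in bold, with a recording rule. Staff record AEs classified 1) "as possibly, probably, or definitely related to study participation and as unexpected or 2) as serious". Four further statements in that section bear on the same question.

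- On expected events: "Information on expected AEs will be recorded on study data collection forms". The limit that follows concerns reporting to the IRBs and NIH.
- On non-serious events: "Non-serious AEs will be recorded on data collection forms but do not require expedited reporting", with an exception for unanticipated problems (UPIRTSO).
- On who classifies: "Study personnel will report any AE to the PI, who will determine 1) its relatedness to study participation and 2) its seriousness".
- On whose events count, the definition refers to an "abnormal laboratory result that a study participant experiences during the course of a study".

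Expectedness is judged against the DMPA package insert, with no separate reference for the arm that receives no injection.

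Sections V.A and V.D blind participants and study staff to DMPA versus placebo, and state that nobody is blinded to open control. Under Section VI.F, "the DSMC will review the accumulated data after an initial subset of participants have been enrolled" and again at half enrollment, with no specific stopping guidelines.

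**The concern.** A reader cannot tell from Section VI.E which AEs go on the forms. The trial enrolls at OSUWMC and at Emory-affiliated hospitals. One site could apply the opening sentence and another the later ones, and each could point to the protocol in support.

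The choice matters because the opening rule makes relatedness a condition of recording. The PI makes that call, and for one of the three arms it is made knowing that no injection was given. A non-serious event could then be recorded after an injection, while a similar event in open control is judged unrelated and dropped. A difference in recorded rates would then partly reflect the filter.

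The second strand is the infant. Section V.A counts woman-infant pairs, Objective 1 includes infant growth and body composition, and Section VI.C refers to infant development. The AE definition does not say that an event in the infant is an AE. The DSMC judges safety from accumulated data, so it depends on what was recorded and for whom.

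**Working it through.** The plan states no figure on this point. The check is a comparison of the sentences, followed by an illustration on assumed rates.

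**1. Which events each rule captures (Section VI.E).**

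| Class of event | Opening rule | Later sentences |
|---|---|---|
| Serious, any relatedness or expectedness | recorded | goes to the PI, expedited |
| Non-serious, related, unexpected | recorded | recorded |
| Non-serious, related, expected | not recorded | recorded |
| Non-serious, unrelated, expected | not recorded | recorded |
| Non-serious, unrelated, unexpected | not recorded | recorded |

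The rules agree on serious events and on one of the four non-serious classes. They disagree on the other three. A non-serious bleeding irregularity, which is on the section's own list of expected events, is an example.

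**2. Where allocation can enter.** Under the opening rule an expected non-serious event is dropped in every arm, because the package-insert list is the same for all. That loses events without favoring an arm. Arm dependence enters only through the relatedness call on unexpected non-serious events. DMPA and placebo are blinded, so the call should act alike in those two arms. Open control is not blinded. The exposed comparison is therefore injection arms (143 + 143 = 286) versus open control (143).

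**3. Illustration. All rates and shares here are assumptions; the documents give none.** Let the true non-serious AE rate be the same in every arm, and let the pass share be the fraction of those events that the filter lets through.

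Recorded rate = true rate × pass share.

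Take a true rate of 20%, with pass shares of 50% (injection) and 25% (open control). Recorded rates are 0.20 × 0.50 = 10% and 0.20 × 0.25 = 5%. The chance of a two-sided p < 0.05 is Φ[(|d| − 1.96 × SE₀)/SE₁].

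- d = 0.10 − 0.05 = 0.05.
- Pooled rate = (286 × 0.10 + 143 × 0.05)/429 = 0.0833.
- SE₀ = √[0.0833 × 0.9167 × (1/286 + 1/143)] = 0.0283.
- SE₁ = √[0.10 × 0.90/286 + 0.05 × 0.95/143] = 0.0254.
- Φ[(0.05 − 0.0555)/0.0254] = Φ(−0.22), about 41%.

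| True rate | Pass share, injection / open | Recorded, injection / open | Chance of spurious p < 0.05 |
|---|---|---|---|
| 10% | 30% / 15% | 3% / 1.5% | 12.7% |
| 20% | 50% / 25% | 10% / 5% | 41.5% |
| 30% | 50% / 10% | 15% / 3% | 98.8% |

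The normal approximation is rough in the first row, where 1.5% of 143 is about two events. With equal pass shares the filter creates no spurious difference. If the later sentences govern, the filter does not operate.

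**4. Whether the infant is covered.** The eligibility criteria and consent steps in Sections V.B and V.D are addressed to women, and the four-month visit is described as the participant returning with her infant. On that usage the AE definition covers the woman. Two texts reach further. The seriousness criteria include a birth defect, but this applies only to serious events. UPIRTSO can involve people other than participants, but only for unexpected matters that indicate harm or raised risk, and the PI decides. A routine non-serious infant event that meets neither test has no stated place on the forms.

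**The case against.** The best defense is that the opening sentence is a loose summary of what is passed on, and that the later sentences are the operating rules. They say that expected and non-serious events are recorded, and every AE goes to the PI before relatedness is judged. The limits attached to them concern reporting to the IRBs and NIH. On that reading no event is filtered out by relatedness. This is plausible and may be what was intended, but the opening sentence is itself worded as a recording rule and nothing says which prevails.

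Relatedness is also judged against study participation and not against the injection, so an open-control event is not automatically unrelated. This weakens the expected imbalance. It does not remove it, because the assessor still knows that no injection was given.

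A reader might infer four stronger points that the documents do not support.

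- That safety data would not be comparable across the arms. Blinding protects DMPA versus placebo, serious events are recorded in every arm, and the problem arises only if the opening rule governs.
- That infants are followed only through growth. Feeding outcomes are collected, and the birth-defect criterion and UPIRTSO wording give a partial route.
- That consent leaves infants out. The consent pages were removed from the text under review, so this cannot be judged.
- That the DSMC will lack event tables by arm. The DSMC is to write its own Charter, which is not available here. The absence of stopping guidelines is a stated choice.

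Fuller recording also has a price. The plan deliberately keeps its instruments short to limit fatigue and response error.

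**Conclusion.** The contradiction is on the face of Section VI.E and needs no assumption: three of four non-serious classes are excluded by one rule and included by the others. The consequence for comparability is conditional. It requires that the opening rule be followed, concerns non-serious events only, and mainly affects the injection arms versus open control. The DMPA-versus-placebo comparison, which isolates the drug, should lose events without being tilted.

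The size cannot be fixed from the documents. The illustrative range of about 13% to 99% shows only that unequal pass shares can produce an apparent difference where none exists. It is not an estimate for this trial. Section V.E describes no between-arm AE analysis, so the exposure lies in monitoring and in any safety summary, not in the primary noninferiority test.

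For infants the finding is one of unclear coverage: serious events and unanticipated problems have a partial route, and other non-serious events have none stated. The point should be corrected, but does not undermine the trial's main result.

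**What to change.** Two wording changes in Section VI.E.

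1. Reword the opening rule to agree with the later sentences: AEs are recorded in the same way in all three arms, whatever their relatedness or expectedness. Relatedness, expectedness and seriousness then act only as filters on onward reporting to the IRBs and NIH.
2. In the AE definition, replace the reference to a study participant with participant or her infant.

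The cost is protocol text, more non-serious records to file and classify, and some added form content. The last is real: the Follow up text in Section V.D describes the questionnaire as covering breastfeeding, contraception and infant measurements, and lists no AE items. Any added items should be few and identical across arms, in keeping with the plan's aim of short instruments.
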